7.4 Follow-up, Day 8 post each vaccination

Day 8 (+2), 36 (+2), 64 (+2), 176 (+2)

Follow-up visits are scheduled in reference to study vaccination date as indicated for each visit window, see Appendix A, SOE. All Treatment Arms will return on D8 (V2), D36 (V4), D64 (V6) and D176 (V10).

- Interim medical history will be obtained by interview of subjects to ensure continued eligibility. Any changes since the previous clinic visit or contact will be noted at each clinic visit.
- All concomitant medications (including solicitation for receipt of any non-study vaccines) will be recorded on the appropriate data collection form at each clinic visit. Any new concomitant medications taken since the last clinic visit or phone contact will be reviewed with subjects and assessed for continued eligibility.

- A targeted physical examination may be performed, if indicated based on review of complete medical history and any updates obtained by interview of subjects, by a study clinician listed on the Form FDA.
- Venous blood will be collected for safety labs.
- All AEs and SAEs will be collected and recorded on the appropriate data collection form at each clinic visit.
- Memory aid information will be reviewed with subjects at each clinic visit.

7.5 Follow-up, Day 29 post each vaccination Day 85, 197

Follow-up visits are scheduled in reference to study vaccination date as indicated for each visit window, see Appendix A, SOE. All Treatment Arms will return 28 days post vaccination on D85 (V7) and D197 (V11).

- Interim medical history will be obtained by interview of subjects to ensure continued eligibility. Any changes since the previous clinic visit or contact will be noted at each clinic visit.
- All concomitant medications (including solicitation for receipt of any non-study vaccines) will be recorded on the appropriate data collection form at Day 85 and Day 197 visit. Any new concomitant medications taken since the previous clinic visit or contact will be reviewed with subjects and assessed for continued eligibility.
- A targeted physical examination may be performed, if indicated based on review of complete medical history and any updates obtained by interview of subjects, by a study clinician listed on the Form FDA 1572.
- Venous blood will be collected for ANDV PRNT and PsVNA antibody assays.
- Venous blood will be collected for future exploratory assays
- Venous blood will be collected for ICS and LPA cellular assays.

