8.2 Laboratory Evaluations

8.2.1 Clinical Laboratory Evaluations

Serum pregnancy tests will be done at the screening visit and processed locally by the site laboratory at the screening visit and a urine pregnancy test will be performed within 24 hours prior to study vaccination on all females of childbearing potential. Urine will be collected in a

sterile urine cup for processing by research staff using a CLIA waived urine pregnancy test kit. Results must be negative and known prior to randomization on Day 1 and prior to administration of study vaccination on Day 29, Day 57 and Day 169.

Clinical screening laboratory tests will be performed at the screening visit and processed by the local (clinical) laboratory. Parameters to be evaluated to confirm trial eligibility as per Section 5.1 and Appendix B, include the following:

- Hematology: WBC, Hgb, platelet count, ANC, and HgbA1c.
- Biochemistry: Total bilirubin, ALT, creatinine, sodium, and potassium. BUN will be done if creatinine is above the normal range.
- Serum serology testing for HIV – 1/2 antibody, HCV antibody, and HBsAg.
- Serum β HCG pregnancy test (all females of childbearing potential) at screening and urine pregnancy test as described above.
- Urinalysis will be done to test for urine protein via dipstick in the clinic. Clean-catch, mid-stream, urine specimen will be collected in a sterile urine cup.
- Urine test for opiates: A clean-catch, mid-stream urine specimen will be collected in a sterile urine cup and transported to the clinical laboratory for processing and examination.

Clinical safety labs will be performed at Day 1 and 169, and approximately 7 days after each study vaccination. If they are abnormal, tests will be repeated at the next scheduled visit (or sooner if medically indicated) and followed to normal or stabilization. Clinical safety laboratory parameters to be evaluated will include WBC, Hgb, platelet count, ANC, sodium, potassium, Creatinine, total bilirubin and ALT. These evaluations will be performed by the local (clinical) laboratory and will not be used for screening purposes prior to dosing.

The volume of venous blood to be collected for clinical screening, immunologic assessments and safety laboratory evaluations is presented in the tables below:

Table 2: Blood Volume (mL) – All Treatment Arms

Study Visit (V)	00	01	02	03	04	05	06	07	08	09	10	11	12	13	U/S or ET
Study Day and Window	Screen	D1	D8	D29	D36	D57	D64	D85	D141	D169	D176	D197	D253	D337	

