9 ASSESSMENT OF SAFETY

9.1 Specification of Safety Parameters

Safety will be assessed by the occurrence of:

1. Serious adverse events occurring from the time of study vaccination through approximately 6 months after the last study vaccination.
2. Solicited Adverse Events – reactogenicity events occurring from the time of study vaccination through 7 days after each study vaccination:
 - a) Local AEs including pain, tenderness, erythema (redness), induration (hardness/swelling), bruising and skin discoloration.
 - b) Systemic AEs including fever, feverishness (chills, shivering, sweating), fatigue (tiredness), malaise (general unwell feeling), myalgia (body aches/muscular pain), nausea, dizziness and headache.
3. Clinical safety laboratory adverse events occurring from the time of study vaccination through approximately 7 days after each study vaccination. Parameters to be evaluated include WBC, Hgb, platelet count, ANC, sodium, potassium, Creatinine, total bilirubin and ALT.
4. Unsolicited Adverse Events –non-serious adverse events occurring from the time of study vaccination through approximately 28 days after the last study vaccination.

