9.3 Reporting Procedures

Solicited local and systemic AEs will be documented and reported from the time of study vaccination through 7 days after each study vaccination.

Clinical safety laboratory adverse events will be documented and reported at Day 1, 169 and 7 days after each study vaccination. Additional safety labs will be reported if the subject returns to the clinic for re-evaluation of abnormal laboratory values through 7 days after the last study vaccination.

Unsolicited non-serious AEs will be documented and reported from the time of study vaccination through approximately 28 days after the last study vaccination.

SAEs (including lab values that meet SAE criteria) will be documented and reported from the time of study vaccination through approximately 6 months after the last study vaccination.

At any time after completion of this trial, if the site principal investigator or appropriate sub-investigator becomes aware of an SAE that is suspected to be related to study product, the site principal investigator or appropriate sub-investigator will report the event to the DMID Pharmacovigilance Group.

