9.5 Halting Rules

9.5.1 Sentinel Subject Halting Rules

If any of these conditions are met, further vaccinations will be halted pending SMC electronic review.

9.5.1.1 If none of the following conditions are met, may proceed to the second sentinel subject:

- Any SAE regardless of the relationship to the study product
- Any laryngospasm, bronchospasm, or anaphylaxis within 1 day after administration of study product that is considered related to study product.
- One Grade 3 unsolicited adverse event that is considered related to study product.

9.5.1.2 If none of the following conditions are met, may proceed to the remainder of the cohort:

- Any SAE regardless of the relationship to the study product
- Any laryngospasm, bronchospasm, or anaphylaxis within 1 day after administration of study product that is considered related to study product.
- Any generalized urticaria after administration of study product that is considered related to study product.

- One Grade 3 unsolicited adverse event that is considered related to study product and not resolved or improved to lower grade within 2 days.
- Same Grade 2 or higher solicited local adverse event in both sentinel subjects that is considered related to study product and not resolved or improved to lower grade within 2 days.
- Same Grade 2 or higher solicited systemic adverse event in both sentinel subjects that is considered related to study product and not resolved or improved to lower grade within 2 days.
- Same Grade 2 or higher laboratory adverse event in both sentinel subjects that is considered related to study product.

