9.5.2 Study Halting Rules

Further enrollment and study vaccinations will be halted for SMC review/recommendation if any of the following are reported:

- Any subject experiences a study product-related SAE from the time of the study product administration through the subject's last study visit.
- Any subject experiences laryngospasm, bronchospasm, or anaphylaxis within 1 day after administration of study product that is considered related to study product.
- Two or more subjects experience generalized urticaria (defined as occurring at more than two body parts) after administration of study product that is considered related to study product.
- Two or more subjects experience a grade 3 unsolicited AE (in the same MedDRA High Level Term) after administration of study product that is considered related to study product and not resolved or improved to lower grade within 2 days.

This trial will also be halted for SMC review/recommendation if, within 7 days after administration of any study vaccination, any of the following occurs:

- Two or more subjects experience the same grade 3 solicited local adverse event that is considered related to study product and not resolved or improved to lower grade within 2 days.
- Two or more subjects experience the same grade 3 solicited systemic adverse event that is considered related to study product and not resolved or improved to lower grade within 2 days.

- Two or more subjects experience the same grade 3 laboratory adverse event that is considered related to study product.

Grading scales for solicited local (application site) and systemic (subjective and quantitative) AEs are included in Section 9.2.2

Grading scales for clinical safety laboratory adverse events are included in Section 9.2.2.

If any of the halting rules are met following any subject receipt of any study vaccination, then this trial will not continue with the remaining enrollments or study vaccinations without a review by and recommendation from the SMC to proceed.

DMID retains the authority to suspend additional enrollment and study interventions/administration of study product during the entire trial, as applicable.

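### As written, the laboratory halting rule stops counting 7 days after a dose, but the scheduled safety labs may be drawn 7, 8 or 9 days after it

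*Protocol*

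**What the plan says.** Protocol Section 9.5.2 has two lists of study halting rules. The second is introduced by the condition "within 7 days after administration of any study vaccination, any of the following occurs". It holds two bullets on solicited events and one on laboratory events: "Two or more subjects experience the same grade 3 laboratory adverse event that is considered related to study product". No tolerance is attached to the 7 days.

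Section 7.4 sets the post-dose visits at which safety labs are drawn: "Day 8 (+2), 36 (+2), 64 (+2), 176 (+2". It anchors them to the dose: "Follow-up visits are scheduled in reference to study vaccination date as indicated for each visit window, see Appendix A, SOE". Appendix A labels the day of each dose as Day 1 and gives the following safety visit as Day 8 +2, with no allowance for an earlier visit.

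Other sections describe the same labs more loosely:

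- Section 8.2.1: "Clinical safety labs will be performed at Day 1 and 169, and approximately 7 days after each study vaccination".
- Section 9.1: "Clinical safety laboratory adverse events occurring from the time of study vaccination through approximately 7 days after each study vaccination".
- Section 9.3: "Clinical safety laboratory adverse events will be documented and reported at Day 1, 169 and 7 days after each study vaccination".
- Section 9.5.1.2, the sentinel rule: "Same Grade 2 or higher laboratory adverse event in both sentinel subjects that is considered related to study product". This bullet carries no day limit of its own.

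**The concern.** A halting rule should cover every result its own schedule can produce. Here the visit window runs two days past the rule's limit, so whether a result counts can depend on which permitted day the subject attends.

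Take two vaccinated subjects, each with a related ALT above 245 unit/L (grade 3 in Protocol Table 9) at the safety visit after the same dose. If both attend 7 days after the dose, the rule is met and dosing stops for committee review. If one attends a day later, still in window, the rule as written is not met. The biology and the compliance are the same, but the instruction differs.

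This is a first-in-human trial, and its halting rules exist so that a pause does not depend on discretion. What is at stake is a binding rule that may fail to fire on compliant data.

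**Working it through.** **Inputs.** Dose days 1, 29, 57 and 169 (Protocol Section 4). Safety visits on Days 8, 36, 64 and 176, each with an offset of 0, 1 or 2 days (Section 7.4 and Appendix A). Rule limit of 7 days (Section 9.5.2).

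**Formula.** Days after dose = visit day + offset − dose day. A result counts as written if this is 7 or less, taking the draw date as the event date.

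**Nominal timing first.** Section 4 says the labs are taken 7 days after each vaccination. With offset 0: 8 − 1 = 7, 36 − 29 = 7, 64 − 57 = 7 and 176 − 169 = 7. The plan's figure is reproduced for all four doses.

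**With the permitted window.**

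| Dose day | Visit day | Offset 0 | Offset 1 | Offset 2 |
|---|---|---|---|---|
| 1 | 8 | 7 | 8 | 9 |
| 29 | 36 | 7 | 8 | 9 |
| 57 | 64 | 7 | 8 | 9 |
| 169 | 176 | 7 | 8 | 9 |
| Within 7 days? | | yes | no | no |

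A dose given late within its own window does not change this, because the safety visit moves with the dose. One of the three permitted days is inside the rule. That is a count of days, not a share of draws: the share drawn on days 8 or 9 could be anything from none to all.

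**Other draws.** The remaining scheduled safety draws are before dose 1 and before dose 4. The latter is nominally 169 − 57 = 112 days after dose 3, so neither closes the gap. An unscheduled safety draw within 7 days (Section 7.9) would count, but it is not routine.

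**Time limits within 9.5.2.** Related serious events count through the last visit. Laryngospasm, bronchospasm and anaphylaxis count within 1 day. Generalized urticaria and unsolicited grade 3 events have no day limit. Since limits vary by bullet, a reader will take the 7 days as a real limit. It suits the solicited bullets, which match the 7-day memory aid. It does not suit a blood test whose first permitted day is day 7.

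**The case against.** The strongest reply is that the protocol uses 7 days as a name for this visit. The laboratory primary outcome in Section 3.2.1, the design text in Section 4 and the reporting text in Section 9.3 all do so, and Sections 8.2.1 and 9.1 say approximately. On that reading 9.5.2 already includes days 8 and 9. This carries weight as evidence of intent. It does not supply the missing words in the rule that must be applied.

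The sentinel contrast is weaker than it looks. Section 9.5.1.2 sets no day limit on its laboratory bullet, but Section 4 has sentinels followed through Day 8, so it says little about what 9.5.2 meant.

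There are real safeguards. The safety committee must review the 2 mg cohorts before 4 mg begins. Section 5.4.3 withholds a subject's next dose if a grade 3 value has not fallen to grade 1 or less. The sponsor can suspend dosing at any time, and ad hoc committee meetings can be called. These stand, with limits. The committee review is itself defined through 7 days after dose 2, and 2 mg dosing may continue meanwhile. The next-dose block protects one subject and does not halt the trial. The other two are discretionary.

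A late result might also count under the unsolicited-event rule, since Section 9.2.1 includes abnormal laboratory findings among adverse events. But Section 9.1 lists laboratory events separately from unsolicited ones, and that rule requires no improvement within 2 days, whereas 8.2.1 repeats abnormal labs at the next scheduled visit unless medically urgent. This route is possible but unsettled.

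Finally, 9.5.2 gives no convention for dating a laboratory event, and the safety committee charter and the Manual of Procedures, which might define the window, are not among the documents.

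**Conclusion.** The point holds as a defect of wording in a binding rule. Compliant laboratory results from 8 and 9 days after a dose are outside 9.5.2 as written, if the event is dated by the draw. They were probably meant to count. The practical risk is modest, and confidence is medium because of the dating assumption and the documents not seen. It should still be corrected, since following the text exactly could leave a halt uncalled.

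Three stronger conclusions might be inferred, and the documents support none of them:

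- **That laboratory outcome data are lost.** The samples are taken and graded, and the SAP laboratory tables report them by visit. Only their status under the halting rule is in doubt.
- **That the gap can be sized by counting planned post-vaccine draws that lack a scheduled committee review.** Such a count includes day 7 draws, which the rule covers, and credits the committee review and sentinel rule on a looser reading of their timing than it allows 9.5.2. Stressing dose 4, after which the next-dose block has no effect, adds little: a halt protects only subjects with doses left.
- **That the chance of a halt falls by a stated amount.** Any such figure needs a grade 3 event rate and a distribution of attendance days, and the documents give neither.

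**What to change.** In Protocol Section 9.5.2, take the laboratory bullet out of the 7-day list and apply it to results through the Day 8 (+2) post-vaccination safety visit, that is, the Day 8, 36, 64 or 176 visit. Leave the solicited local and systemic bullets at 7 days.

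The cost is one sentence in a short amendment, which needs IRB approval before use (Protocol Section 14.2). No samples, visits, staff or tables are added.

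SAP Section 4.3.3 describes Cohorts 3 and 4 as already randomized, so an amendment may reach only the remaining doses. If dosing is complete, the clinical study report should state whether any related grade 3 laboratory results from 8 or 9 days after a dose were counted toward the rule, and successor protocols should carry the corrected wording. SAP Tables 106 and 107 already list severity, relationship and actual study day. With the dosing dates, that is enough to answer the question without new data.

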9.6 Safety Oversight (ISM plus SMC)

9.6.1 Independent Safety Monitor (ISM)

An ISM is a physician with relevant expertise whose primary responsibility is to provide to DMID an independent safety assessment in a timely fashion. Participation is for the duration of the DMID study and is a voluntary position that does not receive payment. The ISM must meet the requirements of the NIAID conflict of interest policy.

The ISM:

- Is in close proximity to the study site and has the authority and ability to readily access study participant records in real time.
- May be a member of the participating institution's staff but preferably be from a different organizational group within the institution.
- Should not be in a direct supervisory relationship with the investigator.
- Should have no direct involvement in the conduct of the study.

The ISM will:

- Sign a Conflict of Interest (COI) certification at the time they are asked to participate and provide updates to this information as needed.
- Receive reports of Serious Adverse Events (SAEs) from the site investigator and will be notified by email when DMID is notified of the SAE.

- Evaluate the SAE and report their clinical assessment to DMID, through DMID-CROMS SOCS in a timely manner using the attached report form and email the report to DMID-CROMS SOCS.
- Communicate with the investigator at the site as needed.
- Review additional safety related events at the request of DMID.
- Provide additional information to DMID and/or the SMC by teleconference as requested.

9.6.2 Safety Monitoring Committee (SMC)

This clinical study will utilize an SMC, which is an independent group of experts that advises DMID. The primary responsibility of the SMC is to monitor subject safety. The SMC is external to the DMID and comprises at least 3 voting members. The SMC will consist of members with appropriate phase 1 study expertise to contribute to the interpretation of the data from this trial. Its activities will be delineated in a SMC charter that will describe the membership, responsibilities, and the scope and frequency of data reviews. The SMC will operate on a conflict-free basis independently of the study team. The DMID or the SMC may convene ad hoc meetings of the SMC according to protocol criteria or if there are concerns that arise during the study.

The SMC will review the safety data at the following milestones:

- Organizational meeting (prior to start of the study)
- Data Review meeting (DRM) will be held if any sentinel halting rules are met for Cohort 1 and 2 sentinel subjects. The SMC will conduct an electronic review of available safety data for the first 2 sentinel subjects in Cohorts 1 and 2 (2 mg dose group) that have completed 7 days of the safety assessment after receiving study product. No new subjects may be enrolled during this follow-up and review period, but screening may continue.
- DRM: The SMC will conduct a review of available safety data for the first 24 subjects in Cohort 1 and 2 (2 mg dose group) that have completed 7 days of the safety assessment after receiving the second dose of study product. No new subjects may be enrolled during this follow-up and review period, but screening for Cohort 3 and 4 and vaccination of the remaining doses in Cohorts 1 and 2 may continue.
- DRM will be held if any sentinel halting rules are met for the Cohort 3 and 4 sentinel subjects. The SMC will conduct an electronic review of available safety data for the first 2 sentinel subjects in Cohort 3 and 4 (4 mg dose group) that have completed 7 days of the safety assessment after receiving study product. No new subjects may be enrolled during this follow-up and review period, but screening may continue.

- An Ad Hoc meeting will be convened when a halting rule is met, or at the request of the investigator and/or DMID if there are safety concerns during the course of the study.
- Final review meeting: approximately 6 to 8 months after final clinical database lock to review the cumulative safety and immunogenicity data for this trial. The data will be provided in a standard summary format. The SMC may be asked to provide recommendations in response to questions posed by DMID.

The SMC will operate under the rules of a DMID-approved charter that will be written at the organizational meeting of the SMC. At this time, each data element that the SMC needs to assess will be clearly defined. Procedures for SMC reviews/meetings will be defined in the charter. The SMC will review applicable data to include, but not limited to, study progress and participant clinical, safety, and reactogenicity data. Reports may include enrollment and demographic information, medical history, concomitant medications, physical assessments, clinical laboratory values, dosing compliance, and solicited and unsolicited AE/SAEs. Additional data may be requested by the SMC, and interim statistical reports may be generated as deemed necessary and appropriate by DMID. The SMC may receive data in aggregate and presented by cohort. The SMC may also be provided with expected and observed rates of the expected AEs in an unblinded fashion, and may request the treatment assignment be unblinded for an individual subject if required for safety assessment. The SMC will review grouped and unblinded data in the closed session only. The SMC will meet and review this data at scheduled time points or ad hoc as needed during this trial as defined in the SMC charter. As an outcome of each review/meeting, the SMC will make a recommendation as to the advisability of proceeding with study vaccinations (as applicable), and to continue, modify, or terminate this trial.

DMID or the SMC chair may convene the SMC on an ad hoc basis according to protocol criteria or if there are immediate concerns regarding observations during the course of this trial. The DMID Medical Monitor is empowered to stop enrollment and study vaccinations if adverse events that meet the halting criteria are reported. The DMID Medical Monitor and the ISM (as deemed necessary) will be responsible for reviewing SAEs in real time. The SMC will review SAEs on a regular basis and ad hoc during this trial.

